175 combination therapy (excluding GLP1 receptor agonists) or on low-dose insulin therapy
176 (TDD ≤ 0.4 unit/kg/day) prior to admission.
- 177 4. Subjects with a hospital admission BG < 400 mg/dL without laboratory evidence of diabetic
178 ketoacidosis (serum bicarbonate < 18 mEq/L or positive serum or urinary ketones).
- 179 5. BMI > 25 Kg/m² and ≤ 45 Kg/m²

181 **Exclusion Criteria**

- 182 1. Age < 18 or > 80 years.
- 183 2. Subjects with stress hyperglycemia (BG > 140 mg/dL and HbA1c < 6.5%)
- 184 3. Subjects with a history of type 1 diabetes (1).
- 185 4. Treatment with GLP1 analogs during the past 3 months prior to admission.
- 186 5. Recurrent severe hypoglycemia or hypoglycemic unawareness.
- 187 6. Subjects with gastrointestinal obstruction, gastroparesis or those expected to require
188 gastrointestinal suction.
- 189 7. History of medullary thyroid cancer or multiple endocrine neoplasias
- 190 8. Patients with acute or chronic pancreatitis, pancreatic cancer or gallbladder disease.
- 191 9. Patients with clinically significant hepatic disease (cirrhosis, jaundice, end-stage liver
192 disease, portal hypertension) and elevated ALT and AST > 3 times upper limit of normal, or
193 significantly impaired renal function (GFR < 30 ml/min).

- 194 10. Treatment with oral or injectable corticosteroid (equivalent or higher than prednisone
195 5mg/day), parenteral nutrition and immunosuppressive treatment.
196 11. Mental condition rendering the subject unable to understand the nature, scope, and possible
197 consequences of the study.
198 12. Female subjects who are pregnant or breast-feeding at time of enrollment into the study.
199 13. Females of childbearing potential who are not using adequate contraceptive methods (as
200 required by local law or practice).

201

202 **Investigational drugs.**

203

- 204 • Liraglutide 6.0 mg/mL solution for subcutaneous (s.c.) injection. The solution will be
205 provided in 3 mL prefilled pen.
- 206 • Liraglutide will be provided to patients
- 207 • Glargine will be provided

208

209

210 **Withdrawal Criteria**

211

- 211 1. The subject may withdraw at will at any time.
- 212 2. The subject may be withdrawn from the trial at the discretion of the investigator due to a
213 safety concern or if judged non-compliant with trial procedures or included in contravention
214 to the inclusion and/or exclusion criteria.
- 215 3. Subject diagnosed with acute pancreatitis by clinical and/or radiographic criteria.

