- 216 4. If the fasting BG and average daily BG on 3 consecutive days exceeds > 15.0 mmol/L (240
217 mg/dL). If this occurs, the subject will be called for an unscheduled visit as soon as possible.
218 A confirmatory FPG should be obtained and analyzed by the hospital laboratory. If this FPG
219 exceeds 15.0 mmol/L (240 mg/dL), and no treatable intercurrent cause for the hyperglycemia
220 has been identified, the subject must be withdrawn.
- 221 5. Pregnancy or intention to become pregnant.

222 **Subject Replacement**

223 There will be no replacement of subjects in this trial.

224

225 **Rationale for Study Population**

226 We will recruit patients with poorly controlled T2D (HbA1c \geq 7%-10%) treated with diet and/or
227 oral antidiabetic agents or on low-dose insulin therapy (TDD \leq 0.4unit/kg/day)prior to admission.
228 Patients will be treated with a basal bolus insulin regimen during the hospital stay (standard of
229 care). Prior to hospital discharge, patients will be randomized to receive liraglutide or glargine
230 as monotherapy in treatment of patients treated with low-dose insulin therapy (TDD \leq 0.4
231 unit/kg/day) (or as add-on therapy to the subject's pre-admission OAD regimen.

232

233 We plan to analyze a total of 280 patients (who receive study medication) with T2D at the time
234 of hospital discharge [liraglutide once daily in combination to OADs (n=140) or glargine once
235 daily in combination to OADs (n=140)].
236

237 **GROUP 1. Liraglutide Treatment Group.**

238

239 **▪ Patients receiving no Therapy prior to admission:**

- 240 • Discharge on liraglutide once daily.
 - 241 • Start metformin if A1C \geq 8% and no contraindications.
- 242

243 **▪ Patients receiving OAD prior to admission:**

- 244 • If no contraindication, restart pre-admission OADs according to standard of care and
245 investigator's medical discretion (metformin, sulfonylureas, nateglinide, repaglinide,
246 pioglitazone) in combination to liraglutide.
 - 247 • The total daily dose of insulin secretagogues (sulfonylureas, nateglinides and
248 repaglinide) will be reduced to 50% of pre-admission dose to avoid risk of
249 hypoglycemia.
 - 250 • DPP4-inhibitors will not be used in combination with liraglutide during the study
251 period.
- 252

253 **Liraglutide Titration:**

254 Liraglutide will be administered once daily in accordance with a 3-4 week dose escalation

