255 regimen with weekly increments of 0.6 mg until the maintenance dose of 1.8 mg is reached.
256 Liraglutide will be administered once daily by s.c. injections, either in the abdomen, thigh or
257 upper arm. Injections can be done at any time of the day and irrespective of meals. It is
258 recommended that the time of injection is consistent throughout the trial. Subjects will be
259 instructed to perform an air shot before the first use of a new prefilled pen.
260

261 **GROUP 2. Glargine Group**

262

263 **V.e. Treatment recommendations at discharge:**

264

265 **▪ Patients receiving no Therapy prior to admission:**

- 266 • Discharge on glargine once daily at 50% of total hospital dose
 - 267 • Add metformin if A1C \geq 8% and no contraindications.
- 268

269 **▪ Patients receiving OAD prior to admission:**

270

271

272

- If no contraindication, restart pre-admission OADs according to standard of care and investigator’s medical discretion (metformin, sulfonylureas, repaglinide, nateglinide, pioglitazone) in combination to glargine at 50% of hospital dose.
- The total daily dose of insulin secretagogues (sulfonylureas, nateglinides and repaglinide) will be reduced to 50% of pre-admission dose to avoid risk of hypoglycemia.
- DPP4-inhibitors will not be used in combination with liraglutide during the study period

Algorithm for outpatient glargine insulin dose adjustment:

Insulin Glargine	
If mean FBG > 180 mg/dL for the last 2 consecutive days and no episodes of hypoglycemia (BG <70 mg/dL)	Increase daily dose by 4 IU
If mean FBG > 140 mg/dL for the last 2 consecutive days and no episodes of hypoglycemia (BG <70 mg/dL)	Increase daily dose by 2 IU
If mean FBG between 100 to 140 mg/dL for the last 2 consecutive days and no episodes of hypoglycemia (BG <70 mg/dL)	No Change
If any FBG between 70 – 99 mg/dl	Decrease by 4 IU or 10% of total daily dose
If any FBG or RBG < 70 mg/dl	Decrease by 8 IU or 20% of total daily dose
If any FBG or RBG < 40 mg/dl	Decrease total daily dose by 30%

In hospital Diabetes Education. Prior to discharge, participants will be trained on:

1. Diabetes education if not received within 1 year of admission.
2. ADA targets for fasting and premeal BG between 70 to 130 mg/dL.
3. Use of glucose meters for home glucose self-monitoring (meters may vary at different institutions).
4. Keeping BG records, and will receive a log-book to record glucose tests results.
5. Hypoglycemia recognition and management (see VI.B.)

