6. Insulin administration (if needed).

Follow-up Care:

- If baseline visit was not fully completed at the time of discharge, patients will be scheduled to return for a short in-person visit to complete (body measurements) study procedures within 7 days of discharge. Research team will call to verify correct administration of study medication and availability of medications and glycemic control monitoring supplies.

- 300 • After discharge, a member of the diabetes research team will contact patients via
301 telephone call every 2 weeks for a total of 26 weeks.
- 302 • Patients will be asked to attend the next outpatient clinic visit at 4 weeks of hospital
303 discharge. During this visit, patients will receive 8 weeks drug supply of liraglutide and
304 will be asked to return to clinic at 12 weeks for the next outpatient visit. During this visit,
305 patients will receive 12 weeks (3 months) drug supply of liraglutide and will be asked to
306 return to a fourth and final visit at 26 weeks of hospital discharge.
- 307 • Recommendations on insulin adjustment will be provided to patients at each telephone
308 and clinic visits by a licensed physician (fellow or study physician) (see section Vf).

309 **During follow up we will collect the following information:**

- 310 1. Glycemic control:
- 311 a. Mean daily fasting and premeal blood glucose levels.
- 312 b. HbA1c at 3 and 6 months of discharge
- 313 c. Number of hypoglycemic events
- 314 - **Symptomatic hypoglycemia** is defined as an event with typical symptoms (i.e.,
315 sweating, palpitation, and feeling of hunger) with or without confirmation by
316 plasma glucose <70 mg/dl (3.9 mmol/L).
- 317 - **Severe hypoglycemia** is defined as episodes necessitating assistance and
318 associated with measured plasma glucose < 40 mg/dl (2.2 mmol/L) or with
319 prompt recovery after administration of carbohydrates, glucagon, or other
320 resuscitative actions. These episodes may be associated with sufficient
321 neuroglycopenia to induce seizure or coma. Blood glucose measurements may
322 not be available during such an event, but neurological recovery attributable to
323 the restoration of BG to normal is considered sufficient evidence that the event
324 was induced by low plasma glucose.
- 325
- 326 2. Diabetes treatment:
- 327 a. Number of patients receiving insulin therapy, dosage and compliance.
- 328 b. Use of liraglutide and other oral agents, dosage and compliance.

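### Withdrawal criterion 4 twice equates 15.0 mmol/L with 240 mg/dL, but 15.0 mmol/L is about 270 mg/dL, so between about 240 and 270 mg/dL the call-in visit and withdrawal are mandatory under one printed figure and not under the other.

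*Combined protocol and SAP*

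**What the plan says.** All references are to the combined protocol and SAP.

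Withdrawal Criteria, item 4, works in two steps, and the same pair of figures appears in each.

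- **Trigger.** The rule starts if "the fasting BG and average daily BG on 3 consecutive days exceeds > 15.0 mmol/L (240", with the mg/dL unit on the next line. The consequence is a visit: "If this occurs, the subject will be called for an unscheduled visit as soon as possible".
- **Confirmation.** A fasting plasma glucose (FPG) is then measured by the hospital laboratory. If it "exceeds 15.0 mmol/L (240 mg/dL), and no treatable intercurrent cause for the hyperglycemia" "has been identified, the subject must be withdrawn".

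Two other glucose limits carry both units. They are in the hypoglycemia definitions under Follow-up Care and are repeated under Potential Risks to the Subjects. Symptomatic hypoglycemia refers to "plasma glucose <70 mg/dl (3.9 mmol/L", and severe hypoglycemia to an episode "associated with measured plasma glucose < 40 mg/dl (2.2 mmol/L) or with" prompt recovery after treatment.

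Other limits with a printed unit are in mg/dL alone. Inclusion Criteria, item 4, reads "Subjects with a hospital admission BG < 400 mg/dL without laboratory evidence of diabetic" ketoacidosis. The glargine dose algorithm begins "If mean FBG > 180 mg/dL for the last 2 consecutive days and no episodes of hypoglycemia".

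Withdrawal Criteria, item 2, separately lets the investigator withdraw a patient because of a safety concern, with no glucose limit attached.

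**The concern.** A mandatory patient-level rule needs one threshold. Item 4 prints two figures as though they were the same level in different units, and they do not convert into each other. A patient whose glucose lies between them meets the rule under one figure and not under the other.

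The ambiguity affects both steps. Under the higher figure, a patient in the band need not be called in at all, so the confirmatory FPG that decides withdrawal might never be taken. Under the lower figure, the patient must be called in and, if no treatable cause is found, must be withdrawn. The trial runs at several centres, and withdrawal criteria are checked repeatedly during follow-up according to the Flow Chart. What is at stake is whether the rule is applied in the same way to every patient.

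**Working it through.** **Inputs.** From item 4: 15.0 mmol/L and 240 mg/dL. From the hypoglycemia definitions: 70 mg/dL with 3.9 mmol/L, and 40 mg/dL with 2.2 mmol/L.

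**1. Factor implied by item 4.** Factor = mg/dL ÷ mmol/L = 240 / 15.0 = 16.0. If 15.0 is a rounded value, the range is 240/15.05 to 240/14.95, or 15.95 to 16.05.

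**2. Factor implied by the protocol's other pairs.**

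- 70/3.9 = 17.95; with rounding, 70/3.95 to 70/3.85 = 17.72 to 18.18.
- 40/2.2 = 18.18; with rounding, 40/2.25 to 40/2.15 = 17.78 to 18.60.
- Both pairs together allow 17.78 to 18.18.

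The factor from glucose's molar mass, 18.016, lies inside that range.

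**3. Can rounding explain 16.0?** No. The item 4 range (15.95 to 16.05) does not reach 17.78. Even if 240 were itself rounded to the nearest 10, the largest possible factor is 245/14.95 = 16.4. Conversely, a factor of 16 would turn 70 mg/dL into 70/16 = 4.4 mmol/L and 40 mg/dL into 40/16 = 2.5 mmol/L, where the protocol prints 3.9 and 2.2.

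**4. Correct equivalents, using 18.**

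- 15.0 × 18 = 270 mg/dL.
- 240 / 18 = 13.3 mmol/L.
- Gap: 270 − 240 = 30 mg/dL, or 15.0 − 13.3 = 1.7 mmol/L, which is 30/240 = 12.5% of the lower figure.

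Using only the protocol's own range of factors, 15.0 mmol/L is 15.0 × 17.78 to 15.0 × 18.18, about 267 to 273 mg/dL. The same range puts 240 mg/dL at 13.2 to 13.5 mmol/L. Reading 15.0 as anything from 14.95 to 15.05 widens the first range to 266 to 274 mg/dL, a gap of 26 to 34 mg/dL.

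**5. What the rule then requires.** For a confirmed FPG with no treatable cause:

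| FPG (mg/dL) | FPG (mmol/L, ÷ 18) | Above 240 mg/dL? | Above 15.0 mmol/L? |
|---|---|---|---|
| 239 | 13.28 | no | no |
| 241 | 13.39 | yes: mandatory | no: not mandatory |
| 250 | 13.89 | yes: mandatory | no: not mandatory |
| 260 | 14.44 | yes: mandatory | no: not mandatory |
| 270 | 15.00 | yes: mandatory | no: not mandatory |
| 271 | 15.06 | yes: mandatory | yes: mandatory |

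The same split applies at the 3-day trigger.

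**6. Effect on sample size.** None. The calculation of 124 per group, raised to 140 for attrition, uses the HbA1c margin, its standard deviation, alpha and power. The withdrawal threshold is not an input.

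**The case against.** The strongest reply is that everyone will work in mg/dL. Other glucose limits with a printed unit are in mg/dL, either alone or first, and no part of the document shows a site, meter or laboratory reporting in mmol/L. A sensible reader would probably apply 240 mg/dL. This stands as a reason to think that few decisions would differ in practice, and as a guide to the likely intention. It does not settle the text: in item 4, unlike elsewhere, mmol/L is printed first and mg/dL is in brackets, and nothing says which governs.

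Three stronger readings are tempting, and the documents do not support them.

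- **Opposite orders.** A reader might infer that the two figures tell staff to do opposite things. They do not. One makes withdrawal mandatory; the other leaves it not mandatory under item 4. Neither tells staff to keep the patient in the trial.
- **Unprotected patients.** A reader might infer that patients in the band have no safety stop. Item 2 provides one at any glucose level, at the investigator's discretion.
- **Bias in the primary result.** A reader might infer that the unit error distorts the week-26 HbA1c comparison. Nothing in the documents gives the number of patients in the band, their split by arm, or a direction. Whether withdrawn patients should be followed to week 26 is a separate question that would arise with a correct threshold too. Nor can any bias be called small on the ground that glargine is titrated upwards, because that algorithm covers one arm only.

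**Conclusion.** The inconsistency is certain. It appears twice in item 4 and can be shown from the protocol's own conversions. It concerns a decision threshold: across about 30 mg/dL (26 to 34 mg/dL with all rounding allowed for), the call-in visit and, with no treatable cause, withdrawal are mandatory under one printed figure and not under the other.

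The practical effect cannot be sized. It depends on how many patients reach the band and on which figure each site applies, and the documents give neither. The conclusion assumes only that the mg/dL and mmol/L figures are meant as the same level, as the brackets indicate and as in the protocol's other pairs. Sample size and power are unaffected, and no effect on the primary analysis is claimed. The point is worth correcting because the step is mandatory and the correction is almost free.

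**What to change.** **Main change.** Print one matched pair in both places in item 4. The likelier choice is 240 mg/dL (13.3 mmol/L), because the protocol's other limits are in mg/dL. If the clinicians intend the higher level, print 270 mg/dL (15.0 mmol/L). The choice is clinical. The cost is a one-line edit in two places and a note to sites.

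**Separate and optional.** Item 4 does not say whether a withdrawn patient leaves follow-up, and item 2's wording suggests leaving the trial. The document contains no provision to obtain a week-26 HbA1c from these patients. A short amendment could have item 4 stop study drug only, keep patients who still consent in the scheduled visits through the week-26 HbA1c, and analyse them in their randomised arm. The cost is a few extra follow-up contacts and week-26 values that partly reflect rescue treatment. This suggestion makes no claim about the size or direction of any bias, and the unit correction does not depend on it.

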96 to liraglutide or glargine with or without oral agents at hospital discharge.
97

98 **Endpoints:**

99 **Study Outcomes:**

100 The primary outcome of the study is to determine differences in HbA1c concentration at 26
101 weeks from discharge between liraglutide and glargine insulin therapy.
102

103 The secondary outcome is to compare differences between treatment groups in any of the
104 following measures during the 26 weeks following hospital discharge in patients with T2D:

- 105 • Self-measured blood glucose (SMBG) 7-point profiles
- 106 • Fasting and postprandial BG concentration
- 107 • Incidence rate and number of hypoglycemic events (<70 mg/dl) and severe hypoglycemic
108 events (<40 mg/dl).
- 109 • Percent of patients with 26 week HbA1c $<7.0\%$ and no hypoglycemia
- 110 • Percent of patients with 26 week HbA1c $<7.0\%$ and no weight gain
- 111 • Percent of patients with 12 week HbA1c $<7.0\%$ and no hypoglycemia
- 112 • Change in body weight and BMI

- 113 • Cardiovascular risk factors including changes in blood pressure, heart rate, and lipid
- 114 profile.
- 115 • Total daily dose of insulin
- 116 • Number of emergency room visits and hospital readmissions
- 117 • Acute renal failure during the 26-week follow-up defined as a clinical diagnosis of acute
- 118 renal failure with documented new-onset abnormal renal function (increment in
- 119 creatinine ≥ 0.5 mg/dL from baseline)

120
121

122 **Study type:**

123 The trial is a 26-week, randomized, open label-controlled two-armed, multi-center, multi-
124 national trial investigating the efficacy and safety of liraglutide versus glargine insulin in
125 medicine and surgical patients with T2D after hospital discharge.

126 We will recruit a total of 330 poorly controlled (HbA1c $\geq 7\%$ -10%) patients with T2D treated
127 with diet or oral antidiabetic agents (OAD) or on low-dose insulin therapy (TDD ≤ 0.4
128 unit/kg/day) prior to admission. Patients will be treated with a standard basal bolus insulin
129 regimen during the hospital stay. Prior to hospital discharge, patients will be randomized to
130 liraglutide or glargine with or without oral antidiabetic drugs. After discharge, a member of the
131 diabetes research team will contact patients via telephone call every 2 weeks to assess response
132 to therapy. In addition, patients will be asked to attend an outpatient clinic visit at 2 (optional), 4,

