133 12 and 26 weeks after hospital discharge. Recommendation on insulin dose adjustment will be
134 provided to patients at each telephone contact and clinic visits.

135
136 Recommendation for liraglutide dose escalation will be done every one or two weeks until the
137 maintenance dose of 1.8 mg is reached. Dose escalation can be extended over 2 weeks at the
138 discretion of the investigator in case of gastrointestinal adverse events. Liraglutide and insulin
139 will be add-on to the subject's pre-admission OAD regimen. Dose of OAD should remain
140 unchanged throughout the trial, however dose reduction of insulin and sulfonylurea is allowed
141 due to hypoglycemia.

142
143
144 **Study Groups:**

145 We plan to analyze a total of 280 patients (who receive study medication) with T2D at the time
146 of hospital discharge.

- 147
- 148 • Group 1. Liraglutide once daily in combination to OADs (n=140).
- 149
- 150 ▪ Group 2. Glargine once daily in combination to OADs (n=140).

151
152

153 **Study population:**

154 This will analyze 380 general medicine and surgical patients with a known history of T2D, age
155 18-80, treated with diet alone and/or oral antidiabetic agents including sulfonylureas, repaglinide,
156 nateglinide, DPP4s, SGLT2, or metformin as monotherapy or in combination therapy or on low-
157 dose insulin therapy (TDD ≤ 0.4 unit/kg/day) prior to admission. Subjects will be recruited from 5
158 medical centers in the United States. A total of 300 patients will be recruited at Grady Memorial
159 Hospital, Emory University Hospital and Emory Midtown hospital.

161 **Study Sites:** This study will be performed at Grady Memorial Hospital, Emory University
162 Hospital, Emory University Hospital at Midtown, and 3 institutions in the United States:

- 163 1. MetroHealth Medical Center, Cleveland (PI: [name].)
- 164 2. State University of NY at Buffalo (PI: [name].)
- 165 3. University of Miami, Florida (PI: [name].)
- 166 4. Sanatorio Guemes, Buenos Aires -Argentina (PI: [name])

169 **Inclusion Criteria**

- 170 1. Males or females between the ages of 18 and 80 years discharged after hospital admission
171 from non- ICU general medicine and surgical services (excluding gastrointestinal and
172 cardiac surgeries).
- 173 2. Admission HbA1c between 7% and 10%
- 174 3. Patients with T2D treated with diet alone or with oral antidiabetic agents as monotherapy or in

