- 329 c. Protocol adherence by PCP (diabetes clinic versus PCP)
- 330
- 331 3. Clinical Outcome:
- 332 a. Hospital readmissions
- 333 b. Emergency room visits
- 334
- 335
- 336

337 **7-point self-measured blood glucose profile:**

338 Subjects will be instructed to perform a 7-point SMBG profile three times during the trial within
339 one week prior to site visit on a day where the subject do not anticipate unusual strenuous
340 exercise.

341 **Time-points for 7-point profile:**

342
343 The blood glucose levels should be measured and recorded in the diary (including date, actual
344 clock time and blood glucose value) at the following time points, always starting with
345 measurement before breakfast.

- 346
- 347 • Before breakfast
- 348 • 90 min after the start of breakfast
- 349 • Before lunch
- 350 • 90 min after the start of lunch
- 351 • Before dinner
- 352 • 90 min after the start of dinner
- 353 • At bedtime
- 354
- 355

356 **Body measurements**

357 Body measurements consist of the parameters: Body weight, height, waist circumference, hip
358 circumference and BMI

359 **Body weight:** Body weight should be measured in kilogram or pound, without shoes and only
360 wearing light clothing.

361 **Height:** Height (without shoes) should be measured in centimeters or inches and recorded
362 without decimals.

363 **Waist and hip circumference:** The waist circumference is defined as the minimal abdominal
364 circumference located midway between the lower rib margin and the iliac crest. The hip
365 circumference is defined as the widest circumference around the buttocks. Three consecutive
366 measurements of waist and hip circumference should be taken and recorded. Mean values will
367 be used for result analysis. The waist and hip circumferences will be measured to the nearest 0.5
368 cm (0.2 inches) using a non-stretchable measuring tape.

369 The subject should be measured in a standing position with an empty bladder and wearing light
370 clothing with accessible waist and hip. The tape should touch skin, but not compress soft tissue
371 and twist in tape should be avoided. The subject should be asked to breathe normally and the
372 measurement should be taken when the subject is breathing out gently.

373 **Body Mass Index (BMI):** BMI will be calculated by the formula Body weight (Kg)/m².

374

375

376

377

378 **Assessment for Safety**

379
380
381
382
383
384
385
386
387
388
389
390
391
392
393
394
395
396
397
398
399
400
401
402
403
404

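### No routine glucose self-monitoring frequency is set for both arms, although only glargine dosing depends on home readings, so the BG <70 mg/dl comparison can be biased towards liraglutide

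*Combined protocol and SAP*

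**What the plan says.** **Endpoint.** Specific Aim 1 pairs similar HbA1c with fewer hypoglycaemic events on liraglutide. Study Outcomes lists "Incidence rate and number of hypoglycemic events (<70 mg/dl) and severe hypoglycemic" events, and two composites there require HbA1c below 7.0% without hypoglycaemia. The Sample Size section names hypoglycaemia, again as BG <70 mg/dl, as the leading secondary outcome.

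**A second definition.** The follow-up data list and the safety section describe a symptomatic event by typical symptoms ("sweating, palpitation, and feeling of hunger) with or without confirmation by" a value below 70). The two definitions are not reconciled.

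**Glargine dosing.** The outpatient algorithm works on home values. One row begins "If mean FBG > 180 mg/dL for the last 2 consecutive days and no episodes of hypoglycemia (BG <70 mg/dL"; another is triggered "If any FBG or RBG < 70 mg/dl". Under Study type, insulin dose advice is "provided to patients at each telephone contact and clinic visits".

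**Liraglutide dosing.** Liraglutide Titration sets a "regimen with weekly increments of 0.6 mg until the maintenance dose of 1.8 mg is reached". Study type allows slower escalation for gastrointestinal events. No glucose value enters the rule.

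**Testing common to both arms.** In-hospital education covers "Use of glucose meters for home glucose self-monitoring (meters may vary at different institutions") and a log-book for all. The profile section says "Subjects will be instructed to perform a 7-point SMBG profile three times during the trial within" a week of a site visit. The Flow Chart has fasting BG at weeks 4, 12 and 26. Follow-up Care collects average fasting and premeal glucose in all patients, and withdrawal criterion 4 uses readings on three consecutive days. None of this states how many tests a patient takes per day or week.

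**Analysis.** The trial is open label. Analysis of Secondary Endpoints compares patients with an event and event counts, with no reference to the number of readings.

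**The concern.** A value below 70 without symptoms exists in the data only if the patient tested at that moment. The chance of recording at least one such value, and the count of them, therefore rises with the number of tests. Glargine patients have a treatment reason to test before each contact, and liraglutide patients do not. If glargine patients do test more, the recorded rate falls on liraglutide even when the true risk is the same.

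That is the direction the investigators expect, on the leading secondary outcome and on the two composites. Readings that were never taken cannot be recovered at analysis, so the schedule is best fixed in the protocol.

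**Working it through.** **1. The plan's own power table.** Inputs from the Sample Size section: 35% glargine rate, two-sided Fisher's exact test, alpha 0.05, 140 per arm before 10% attrition, so 140 × 0.9 = 126. Full enumeration of the two binomials at 126 per arm gives power 0.998 / 0.970 / 0.854 / 0.639 at odds ratios 0.2 / 0.3 / 0.4 / 0.5. The plan prints >0.99 / 0.97 / 0.85 / 0.64, so the table reproduces. At odds ratio 0.42 the power is 0.82, against the stated 80%.

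**2. Detection model with no true difference.** Let P_G be the glargine proportion with at least one recorded event (20-35%, from the plan). Two quantities are assumptions, because the documents give neither:
- f, the ratio of liraglutide to glargine readings per patient;
- s, the share of events found through symptoms whatever the testing.

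With equal true risk and independent readings:
- g = s + (1 − s)f
- P_L = 1 − (1 − P_G)^g
- OR = [P_L/(1 − P_L)] / [P_G/(1 − P_G)]

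Example: P_G = 0.35, f = 0.5, s = 0 gives P_L = 1 − 0.65^0.5 = 0.194 and OR = (0.194/0.806)/(0.35/0.65) = 0.45.

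**3. Results at 126 per arm.** Each pair is for P_G = 20% / 35%. False benefit means a significant Fisher test in liraglutide's favour. Two-thirds is 121 of 182 daily readings, f = 0.665.

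| f | s | P_L | OR | False benefit |
|---|---|---|---|---|
| 0.5 | 0 | 10.6% / 19.4% | 0.47 / 0.45 | 49% / 76% |
| 0.5 | 0.5 | 15.4% / 27.6% | 0.73 / 0.71 | 12% / 21% |
| 0.665 | 0 | 13.8% / 24.9% | 0.64 / 0.62 | 21% / 37% |
| 0.665 | 0.5 | 17.0% / 30.1% | 0.82 / 0.80 | 7% / 10% |
| 1 | any | 20% / 35% | 1.00 | about 2% |

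**4. Why these ratios are worth showing.** On the narrowest reading, both arms do only the 3 × 7 = 21 profile readings, and glargine adds two fasting readings per dose-advice contact. With 13 contacts (weeks 2 to 26), glargine has 21 + 26 = 47 readings, or 44 if three coincide with profile readings, so f = 0.45-0.48. With the 8 contacts marked for dose adjustment in the Flow Chart, it has 37 or 34, so f = 0.57-0.62. This is not what the plan prescribes. It shows only that the wording leaves room for such ratios.

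**5. Clustering of events within patients.** Suppose risk varies between patients by a gamma distribution (another assumption). Half testing with s = 0 then gives OR 0.50-0.55 and 38-64% false benefit at shape 0.5 to 1, and OR 0.58-0.65 and roughly 30% at variance 4. Clustering shrinks the figures in step 3.

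**The case against.** The strongest reply is that the plan points to home testing in both arms. Everyone gets meter training, fasting and premeal targets and a log-book. Fasting and premeal averages are collected without restriction by arm, and a withdrawal rule relies on consecutive daily readings. If daily fasting and premeal testing is meant for all, f = 1 and this bias disappears. That insulin patients will test more is a prediction, not a statement in the documents.

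Symptomatic events also need no meter, and their capture is supported in both arms. Patients with hypoglycaemia unawareness are excluded, all are taught to recognise symptoms and asked to call, and hypoglycaemia is recorded at every contact.

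These points stand, and they rule out three stronger readings that a reader might infer:
- *Hypoglycaemia is counted only from home meters.* The endpoint names no source of readings, and the symptomatic definition needs none.
- *The arms share no testing schedule.* The three profiles and the fasting BG at weeks 4, 12 and 26 are common. What is missing is a common routine frequency between them.
- *The data could not separate testing from a drug effect.* The common profiles and the log-books would allow a partial check, if the plan called for one.

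The reply does not supply a routine frequency, say which definition is counted, or bring the number of readings into the analysis.

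**Conclusion.** The concern holds in a limited form. Only one arm has a dosing rule that needs repeated home readings, no routine frequency is set for both arms, and the analysis takes no account of how often patients tested. In an open-label trial this can bias the BG <70 comparison and the two composites towards liraglutide.

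The size is a range. With no true difference, the chance of a false liraglutide benefit runs from about 2% with equal testing to 49-76% at half testing with no capture by symptoms. It falls to 12-21% at half testing if symptoms reveal half of events. Both the testing ratio and the symptom share are assumed, and clustering would lower the figures.

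It would be tempting to conclude that unequal testing alone explains any lower rate on liraglutide. The documents do not support that: reaching the planned odds ratio of 0.42 takes a testing ratio of about 0.45-0.47 with no event found by symptoms. The HbA1c primary outcome is not affected. The point should be corrected, but it does not threaten the main conclusion.

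**What to change.** - State one routine self-monitoring schedule for outcome measurement, identical in both arms. No dosing rule needs to change. If daily fasting and premeal testing is already intended for everyone, say so.
- State which events count in the between-arm comparison and in the composites: BG <70 mg/dl, symptomatic, or both.
- Record and tabulate the number of readings per patient by arm.
- Add a sensitivity analysis limited to readings at the common scheduled times, including the 7-point profiles, plus symptomatic episodes. Keep reporting all BG <70 events, so that genuine unscheduled lows stay visible.

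The cost is protocol wording, one tabulation and one added analysis. Meter training and log-books are already planned for all participants. The downsides are somewhat more test strips and logging in the liraglutide arm, and fewer events, hence less precision, in the sensitivity analysis.
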